#### **8.1.1.4 Postinfusion Medication and Monitoring**

Patients may receive 20 to 25 mg prednisone or 4 mg of dexamethasone PO or equivalent on the first and second days after all full-dose infusions. Other concomitant medications can be administered per institutional protocols.

During the infusion and for 2 hours after the end of infusion, the patient should be continually monitored by medically qualified staff with access to emergency medical equipment and medications to manage infusion reactions.

On days on which the combination agent daratumumab and hyaluronidase-fihj is given on the same visit day as modakafusp alfa, administer the modakafusp alfa-specific postinfusion medications only.

#### **8.1.1.5 Prophylaxis Against Risk of Infection**

Patients may be at an increased risk of infection, including reactivation of herpes zoster and herpes simplex viruses. Prophylactic antiviral therapy, such as acyclovir or valacyclovir, should be initiated as clinically indicated.

### **8.1.2 Combination Agent Daratumumab SC**

#### **8.1.2.1 Dosage**

Daratumumab SC: 1800 mg QW for Cycles 1 and 2, Q2W for Cycles 3 to 6, and Q4W thereafter in 28-day cycles.

#### **8.1.2.2 Administration**

Daratumumab SC will be administered SC before modakafusp alfa on days when both agents are given on the same visit day. At least 30 minutes should elapse between the completion of the injection and the initiation of the infusion of modakafusp alfa.

#### **8.1.2.3      *Premedication***

Before each injection, patients will receive the following premedication approximately 1 to 3 hours before the daratumumab and hyaluronidase-fihj on each dosing day ([Darzalex Faspro \(daratumumab and hyaluronidase-fihj\) 2022](#)).

- Methylprednisolone 100 mg (or approximate equivalent such as dexamethasone 20 mg) PO or IV for the initial injection. Consider reducing the dose of methylprednisolone to 60 mg (or approximate equivalent such as dexamethasone 12 mg) PO or IV following the second dose of daratumumab and hyaluronidase-fihj before subsequent injections.
- Antipyretics: PO acetaminophen 650 to 1000 mg.
- Antihistamine: PO or IV diphenhydramine 25 to 50 mg, or equivalent.

On days when both daratumumab and hyaluronidase-fihj and modakafusp alfa are given on the same visit day, administer the modakafusp alfa-specific premedication only.

#### **8.1.2.4      *Postinjection Medication***

Administer methylprednisolone 20 mg (or an equivalent dose of an intermediate- or long-acting corticosteroid such as dexamethasone 4 mg) PO for 2 days starting from the day after the administration of daratumumab and hyaluronidase-fihj ([Darzalex Faspro \(daratumumab and hyaluronidase-fihj\) 2022](#)).

On days when both daratumumab and hyaluronidase-fihj and modakafusp alfa are given on the same visit day, administer the modakafusp alfa-specific postmedication only.

If the patient does not experience a major systemic administration-related reaction after the first 3 doses of daratumumab and hyaluronidase-fihj, consider discontinuing the administration of corticosteroids (excluding any background regimen specific corticosteroid or in the event when corticosteroid is required as a premedication for the combination drug such as modakafusp alfa).

Note: For any patient with a history of chronic obstructive pulmonary disease, consider prescribing short and long-acting bronchodilators and inhaled corticosteroids. After the first 4 doses of daratumumab and hyaluronidase-fihj, consider discontinuing these additional postmedications, if the patient does not experience a major systemic administration-related reaction ([Darzalex Faspro \(daratumumab and hyaluronidase-fihj\) 2022](#)).

#### **8.1.2.5      *Prophylaxis for Herpes Zoster Reactivation***

Initiate antiviral prophylaxis to prevent herpes zoster reactivation within 1 week after starting daratumumab and hyaluronidase-fihj and continue for 3 months after EOT.

## **8.2      *List of EU Auxiliary Medicinal Products***

- Corticosteroids.
- Analgesics and antipyretics.
- Antihistamines.

- Leukotriene receptor antagonists.
- Antivirals.

### 8.3 DLT (Phase 1 Dose Escalation)

#### 8.3.1 Definitions of DLT

Toxicity will be evaluated according to the NCI CTCAE, Version 5.0.

Patients will be monitored through all cycles of therapy for toxicities. Primarily, only toxicities that occur during Cycle 1 will be used for the purposes of defining DLT.

A DLT will be defined as any of the following events that are considered by the investigator to be at least possibly related to modakafusp alfa:

- Any Grade 5 AE.
- Hematologic toxicity, clearly unrelated to the underlying disease are defined as follows:
  - Nonfebrile Grade 4 neutropenia ( $ANC <0.5 \times 10^9/L$ ;  $ANC <500 \text{ cells/mm}^3$ ) lasting more than 7 consecutive days.
  - Febrile neutropenia: Grade  $\geq 3$  neutropenia ( $ANC <1.0 \times 10^9/L$ ;  $ANC <1000 \text{ cells/mm}^3$ ) with fever and/or infection, where fever is defined as a single episode of body temperature  $>38.3^\circ\text{C}$  ( $101^\circ\text{F}$ ) or sustained temperature  $38.0^\circ\text{C}$  ( $100.4^\circ\text{F}$ ) for more than 1 hour.
  - Grade 4 thrombocytopenia (platelets  $<25,000/\text{mm}^3$ ) lasting more than 14 consecutive days.
  - Grade  $\geq 3$  thrombocytopenia (platelets  $<50,000/\text{mm}^3$ ) with clinically significant bleeding.
  - Any other Grade  $\geq 4$  hematologic toxicity with the exception of Grade 4 lymphopenia.
- Nonhematologic toxicity  $\geq$ Grade 3 clearly unrelated to the underlying disease, **with the exception of:**
  - Asymptomatic laboratory changes (other than renal and hepatic laboratory values) that improve within 72 hours (reversion of Grade 4 events to Grade  $\leq 2$ , reversion of Grade 3 events to Grade  $\leq 1$  or baseline).
  - Grade 3 nausea and/or emesis that can be controlled to Grade  $\leq 2$  in  $\leq 2$  days with the use of optimal antiemetics (defined as an antiemetic regimen that employs both a serotonin receptor subtype 3 antagonist and a corticosteroid given in standard doses and according to standard schedules).
  - Grade 3 elevation in ALT, AST, and/or alkaline phosphatase that resolves to Grade  $\leq 1$  or baseline with supportive care within 7 days and is not associated with other clinically relevant consequences.

- Grade 3 IRR that resolves with appropriate clinical treatment, without recurrence of Grade 3 symptoms.
- Grade 3 fatigue lasting less than 72 hours.
- Grade 3 arthralgia/myalgia that responds to nonsteroidal anti-inflammatory drugs within 7 days.
- Grade 3 diarrhea that can be controlled to Grade  $\leq 2$  in  $\leq 72$  hours with appropriate treatment.
- Grade 3 rash and pruritis that respond to standard treatment and resolve or improve to Grade  $\leq 2$  in  $\leq 72$  hours.
- Delay in the initiation of Cycle 2 by more than 14 days due to a lack of adequate recovery of treatment-related hematological or nonhematologic toxicities.

### 8.3.2 Definition of DLT-Evaluable Patients

The DLT-evaluable population will include patients in the dose escalation/de-escalation phase who either experienced a DLT in Cycle 1 in the treatment phase of the study, or who have completed the Cycle 1 dose of modakafusp alfa and received at least 75% of the planned dose of daratumumab SC.

Patients who withdraw before completing the DLT assessment period for reasons other than a DLT, or who do not fulfill either of the criteria above, will not be evaluable for assessment of DLT for dose review decisions and will be replaced in the cohort.

### 8.4 Dose Escalation Rules (Phase 1 Dose Escalation)

The rolling six design ([Skolnik et al. 2008](#)) will be implemented to guide the dose escalation/de-escalation to evaluate the safety and tolerability of modakafusp alfa in combination with daratumumab SC.

#### *Rolling Six Design*

In the rolling six design, up to 6 patients may be concurrently enrolled into a given dose level. Dose levels will be assigned, as outlined below, on the basis of the number of patients currently enrolled in the cohort, the number of DLTs observed, and the number of patients whose evaluation is pending at the time of new patient entry.

- Three to 6 patients may concurrently be enrolled in the study.
- Accrual to the study may be suspended if there are already 6 patients enrolled at the current dose level but not sufficient information to make the decision for the next action.
- Decisions as to whether to resume enrolling on the next dose level will be made using data available at the time of new patient enrollment.

- De-escalation will occur when 2 or more DLTs are observed at the current dose level regardless the number of patients enrolled. The current dose level will be considered toxic.
- If no more than 1 DLT is observed at the next higher dose level, escalation will occur when 3 of 3, 4 of 4, 5 of 5, 5 of 6, or 6 of 6 patients are enrolled at the current dose level with no DLT observed. If at least 2 DLTs have been observed at the next higher dose level, no escalation is allowed.
- In all other situations, patients will be enrolled and dosed at the current dose level up to a total of 6.

The initial dose level to be evaluated for modakafusp alfa will be 80 mg Q4W (Section 4.3). If 2 or more DLTs are observed at the starting dose level during the 28-day cycle, the dose for modakafusp alfa will be de-escalated to 60 mg Q4W. The modakafusp alfa 120 or 240 mg Q4W doses could be evaluated depending on the observed number of DLTs (observed in Cycle 1 of a 28-day cycle) as well as pending data as illustrated in [Table 8.a](#). Daratumumab SC dosing will be administered according to the daratumumab SC (4-week cycle) prescribing information ([Darzalex Faspro \(daratumumab and hyaluronidase-fihj\) 2022](#)). It is estimated that approximately 18 DLT-evaluable patients will be enrolled in the phase 1 dose escalation and at least 6 DLT-evaluable patients will be enrolled at the modakafusp alfa MTD in combination with daratumumab SC.

The dose escalation/de-escalation will stop when (1) the decision for the next patient is to be dosed at the next higher dose level and the next higher dose level is considered toxic (ie,  $\geq 2$  DLTs observed), or (2) the decision for the next patient is to be dosed at the next higher dose level and the current dose level is the highest dose level planned and 6 patients have already been evaluated, or (3) the decision for the next patient is to be dosed at the next lower dose level and 6 patients have already been evaluated with the next lower dose level, or (4) the decision for the next patient is to be dosed at the next lower dose level and the current dose level is the lowest dose level planned.

The MTD will be claimed as the highest dose level that has 6 evaluated patients with fewer than 2 DLTs.

**Table 8.a Dose Escalation and De-escalation Rules**

No. Patients Enrolled at Current Dose	No. DLTs	No. Without DLT	No. With Data Pending	If MTD Not Exceeded a	If MTD Exceeded b
2	0,1	Any	Any	Stay	Stay
2	2	0	0	De-escalate	De-escalate
3	0	0, 1, 2	3, 2, 1	Stay	Stay
3	0	3	0	Escalate	Stay
3	1	0, 1	2, 1	Stay	Stay
3	1	2	0	Stay	Stay

**Table 8.a Dose Escalation and De-escalation Rules**

No. Patients Enrolled at Current Dose	No. DLTs	No. Without DLT	No. With Data Pending	If MTD Not Exceeded a	If MTD Exceeded b
3	≥2	Any	Any	De-escalate	De-escalate
4	0	0, 1, 2	4, 3, 2	Stay	Stay
4	0	3	1	Stay	Stay
4	0	4	0	Escalate	Stay
4	1	0, 1	3, 2	Stay	Stay
4	1	2	1	Stay	Stay
4	1	3	1	Stay	Stay
4	≥2	Any	Any	De-escalate	De-escalate
5	0	0, 1, 2	5, 4, 3	Stay	Stay
5	0	3, 4	2, 1	Stay	Stay
5	0	5	0	Escalate	Stay
5	1	0, 1	4, 3	Stay	Stay
5	1	2	2	Stay	Stay
5	1	3, 4	1, 0	Stay	Stay
5	≥2	Any	Any	De-escalate	De-escalate
6	0	0, 1, 2	6, 5, 4	Suspend c	Suspend
6	0	3, 4	3, 2	Suspend	Suspend
6	0	5, 6	1, 0	Escalate	MTD
6	1	0, 1	5, 4	Suspend	Suspend
6	1	2	3	Suspend	Suspend
6	1	3, 4	2, 1	Suspend	Suspend
6	1	5	0	Escalate	MTD
6	≥2	Any	Any	De-escalate	De-escalate

DLT: dose-limiting toxicity; MTD: maximum tolerated dose.

a MTD not exceeded: no more than 1 DLT is observed at any dose level.

b MTD exceeded: 2 or more DLTs are observed at any dose level.

c “Suspend” means that enrollment will halt until sufficient DLT data is available to determine the action for the next new patient.

Additional patients are permissible to be enrolled if the stopping rule for dose escalation/de-escalation is not triggered after the last patient has been evaluated.

More conservative dose escalation, evaluation of intermediate doses or different dosing intervals, and expansion of an existing dose level are all permissible after discussions between the sponsor and the investigators if such measures are needed for patient safety or for a better understanding of the dose-related toxicity, exposure, or PD of modakafusp alfa in combination with daratumumab SC.

8.5

## 8.6 Dose Modification Guidelines

### 8.6.1 Modakafusp Alfa

### *8.6.1.1 Intrapatient Dose Escalation*

No intrapatient dose escalation is planned for this study.

#### 8.6.1.2 Criteria for Beginning or Delaying a Subsequent Treatment Cycle

Treatment with modakafusp alfa will use a cycle length of 28 days. For a new cycle of treatment to begin, the patient must meet the following criteria:

- ANC  $\geq 1000/\text{mm}^3$ . Granulocyte-colony stimulating factor can be used to reach this level.
- Platelet count must be  $\geq 50,000/\text{mm}^3$ . Platelet transfusion can be applied any time clinically indicated but should not be applied only for the purpose of meeting the treatment criterion of platelet count.

For therapy to resume, toxicity considered to be related to treatment with modakafusp alfa must have resolved to Grade  $\leq 1$  or baseline (Grade 2 for neutrophil and platelets), or to a level considered acceptable by the physician. If the above-cited criteria for retreatment are not met for a patient, initiation of the next cycle of treatment should be delayed for 1 week. At the end of that week, the patient should be re-evaluated to determine whether the criteria for retreatment criteria have been met.

If there is a delay of a subsequent cycle longer than 2 weeks because of a related AE, the patient may be withdrawn from treatment unless there is clinical benefit as assessed by the investigator, with agreement by the sponsor.

### **8.6.1.3 Criteria for Dose Interruption**

All toxicities that occur during the study will be actively managed following the standard of care unless otherwise specified in the protocol. Patients experiencing AEs attributed to modakafusp alfa may continue study treatment with the same dose, may have modakafusp alfa treatment held, may have their dose reduced, or may be permanently discontinued from the study. Patients who have study drug held because of treatment-related or possibly related AEs may resume study drug treatment after resolution of the AE at the same dose level or at a reduced dose, depending on the nature and severity of the AE and whether it is the first occurrence or is recurrent.

**Table 8.b** and **Table 8.c** provide general dose modification recommendations for nonhematologic and hematologic toxicities, respectively. **Table 8.d** provides dose modification recommendations for bleeding TEAEs to mitigate the risk of fatal hemorrhagic events. If the modakafusp alfa dose is withheld on the basis of these criteria, clinical and laboratory re-evaluation should be repeated at least weekly or more frequently, depending on the nature of the toxicity observed, until the toxicity resolves to Grade  $\leq 1$  or baseline. If there are transient laboratory abnormalities that, based on investigator assessment, are not clinically significant or drug related, continuation of therapy without dose modification is permissible on discussion with the sponsor.

#### **Table 8.b Dose Modification Recommendations for Modakafusp Alfa Nonhematological Toxicities**

*This table does not include guidance for management of bleeding TEAEs and IRRs. Refer to **Table 8.d** for the management of bleeding TEAEs and **Table 8.g** and **Table 8.h** for the management of IRRs.*

Criteria	Action
Grade 1 and 2 AEs	No dose reductions or interruptions. Treat according to local practice.
Grade 3 AEs and asymptomatic Grade 4 laboratory AEs	Hold modakafusp alfa next infusion until resolution to Grade $\leq 1$ or baseline, and then resume treatment. First occurrence: Resume treatment at either the same dose or reduced dose at the discretion of the investigator. Subsequent occurrence: Reduce modakafusp alfa by 1 dose level (see Table 8.e ). If treatment has been held for $>14$ consecutive days without resolution of the toxicity (to baseline or Grade $\leq 1$ ), consider permanently discontinuing study treatment unless there is clinical benefit for the patient as assessed by the investigator and with sponsor's approval.
Grade 4 AEs (except asymptomatic Grade 4 laboratory AEs)	Permanently withdraw the patient from the study, except when the investigator determines that the patient is receiving clinical benefit and has discussed this with the sponsor.

AE: adverse event; IRR: infusion-related reaction; TEAE: treatment-emergent adverse event.

This table does not include guidance for the management of bleeding TEAEs, which is found in **Table 8.d** or for the management of IRRs, which is found in **Table 8.g**, **Table 8.h**, and Section **8.10.1.1**.

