## 6.3 Duration of Study

### 6.3.1 Duration of an Individual Patient's Study Participation

Patients may receive study drug treatment until they experience progressive disease, unacceptable toxicity, or other discontinuation criteria are met.

Patients who discontinue study drug treatment for reasons other than progressive disease will continue PFS follow-up every 4 weeks from the end of treatment (EOT) visit until the occurrence of progressive disease, death, the start of subsequent systemic antineoplastic therapy, study termination, whichever occurs first. OS follow-up continues every 12 weeks until death, study termination, or patient withdrawal.

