#### **8.6.1.5 Criteria for Discontinuation**

In the dose escalation, modakafusp alfa should be discontinued in patients experiencing an AE in Cycle 1 meeting criteria for a DLT for which the investigator considers that retreatment of the patient could be dangerous.

If the next cycle of modakafusp alfa is delayed for >14 days because of modakafusp alfa-related toxicities, study treatment should be discontinued unless the investigator considers that the patient will receive benefit continuing in the study. If treatment discontinuation is determined, the EOT visit should be completed within 30 days (+10 days) after the last administration of modakafusp alfa.

Patients who discontinue modakafusp alfa because of TEAEs assessed by the investigator as related *only* to modakafusp alfa may continue daratumumab SC treatment at the discretion of the investigator and with agreement by the sponsor.

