### **9.8 Discontinuation of Treatment With Study Drug and Patient Replacement**

Study drug must be permanently discontinued for patients meeting any of the following criteria:

- Patient experiences an AE or other medical condition that indicates to the investigator that continued participation is not in the best interest of the patient.

Treatment with study drug may also be discontinued for any of the following reasons:

- AE.
- Protocol deviation.
- Progressive disease.
- Symptomatic deterioration.
- Confirmed pregnancy.
- Study terminated by sponsor.
- Withdrawal by patient.
- Lost to follow-up.
- Other.

Once study drug has been discontinued, all study procedures outlined for the EOT visit will be completed as specified in the SOE ([Appendix A](#)). The primary reason for study drug discontinuation will be recorded on the eCRF.

In the case of study termination by the sponsor, eligible patients may have continued access to modakafusp alfa as described in Section [6.5](#).

Only patients who are withdrawn from treatment during Cycle 1 during the safety lead-in for reasons other than DLT will be replaced.

Note that some patients may discontinue study drug for reasons other than progressive disease before completing the full treatment course; these patients will remain in the study for posttreatment assessments as outlined in the SOE ([Appendix A](#)) until progressive disease occurs.

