## **9.9      Withdrawal of Patients From Study**

A patient may be withdrawn from the study for any of the following reasons:

- Lost to follow-up.
- Study terminated by sponsor.
- Withdrawal by subject.
- Transfer of patient to a long-term safety study, single-patient investigational new drug application, or similar program.
- Death.
- Other.

The consequence of study withdrawal is that no new information will be collected from the withdrawn patient and added to the existing data or any database.

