## **9.11 Posttreatment Follow-up Assessments (PFS and OS)**

Patients who stop treatment for any reason other than progressive disease will continue to have PFS visits. The PFS visits should occur every 4 weeks from the EOT until the occurrence of progression, death, the start of subsequent systemic antineoplastic therapy, study termination, whichever occurs first. OS follow-up continues every 12 weeks until death, study termination, or patient withdrawal. Imaging tests for patients with extramedullary disease should be performed every 12 weeks or if new symptoms suggest progressive disease.

See the SOE ([Appendix A](#)) for appropriate assessments during follow-up.

NOTE: Treatment-related SAEs must be reported to the Global Pharmacovigilance department or designee. This includes deaths that the investigator considers related to study drug that occur during the posttreatment follow-up. Refer to Section [10.0](#) for details regarding definitions, documentation, and reporting of SAEs.

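### Table 8.b takes patients with certain Grade 4 nonhaematological AEs out of the study rather than off treatment, which under Section 9.9 ends their data collection

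*Protocol*

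**What the plan says.** Protocol Table 8.b covers nonhaematological toxicity; bleeding and infusion-related reactions have their own tables. For Grade 4 events other than asymptomatic laboratory findings, the action is: "Permanently withdraw the patient from the study". The exception is a patient whom the investigator judges to be benefiting, after discussion with the sponsor. The row above, for Grade 3 events and asymptomatic Grade 4 laboratory findings, stays at treatment level: if toxicity has not resolved after 14 days of holding, "consider permanently discontinuing study treatment unless there is clinical benefit for the patient".

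The text of Section 8.6.1.3 lists the options for any AE attributed to modakafusp alfa. The last is that patients "or may be permanently discontinued from the study", with no grade attached.

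Section 9.9 defines what leaving the study means: "no new information will be collected from the withdrawn patient and added to the existing data or any database". An adverse event is not among its listed reasons; only the residual category could cover one.

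The follow-up sections say:

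- Section 6.3.1: "Patients who discontinue study drug treatment for reasons other than progressive disease will continue PFS follow-up every 4 weeks".
- Section 9.8, which does list an AE as a reason to stop study drug: "these patients will remain in the study for posttreatment assessments".
- Section 9.11: "Patients who stop treatment for any reason other than progressive disease will continue to have PFS visits".

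Section 8.6.1.5 adds that patients who stop modakafusp alfa for events related only to that drug "may continue daratumumab SC treatment at the discretion of the investigator and with agreement by the sponsor".

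**The concern.** The protocol separates stopping drug (9.8) from leaving the study (9.9), and SAP 6.2 tabulates treatment status and study status separately. Table 8.b puts a toxicity event in the second category, where data collection ends.

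Taken literally, the table would affect four kinds of data:

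- **Response.** SAP 6.6.1.2 needs two consecutive adequate assessments to confirm a response and counts assessments made after treatment discontinuation. A patient withdrawn after a single PR, or before a late response, could be counted as a non-responder for ORR, the phase 2a primary endpoint.
- **PFS and OS.** The patient would be censored at the last adequate assessment for PFS and at the date last known alive for OS (SAP 6.6.2.1 and Table 1). Severe toxicity would be the trigger, so the censoring may be informative.
- **Safety.** Recording of AEs through 30 days after the last dose could be cut short in patients with the worst toxicity. TEAE frequency and severity is a phase 1 primary endpoint.
- **Daratumumab SC.** A patient withdrawn from the study cannot use the option in 8.6.1.5.

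**Working it through.** This is mainly a consistency check. The plan gives no figure for it to reproduce.

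**1. Level at which each toxicity rule acts**

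| Place in protocol | Situation | Level |
|---|---|---|
| Table 8.b, upper row | Grade 3, or asymptomatic Grade 4 laboratory AE, unresolved after more than 14 days | Study treatment |
| Table 8.b, lower row | Other Grade 4 nonhaematological AE | **Study** |
| Section 8.6.1.3, text | Any AE attributed to modakafusp alfa | **Study** (one of several options) |
| Table 8.c | Haematological AE, next cycle delayed more than 14 days | Study treatment |
| Table 8.d | Grade 4 bleeding | Modakafusp alfa |
| Table 8.h | Any Grade 4 infusion-related reaction | Treatment |

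Only the lower row of Table 8.b and the 8.6.1.3 text act at study level.

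**2. What follows from each reading**

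- *Study withdrawal:* 9.9 applies and no new data are recorded. This conflicts directly with 6.3.1, 9.8 and 9.11 on PFS visits. It also conflicts with 10.2 and 10.3, which require SAEs to be followed to resolution or a stable outcome.
- *Treatment discontinuation:* 9.8 applies. The patient has the end-of-treatment visit and then PFS visits every 4 weeks and OS contacts every 12 weeks. Nothing conflicts.

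OS is a partial case. By their own terms, 6.3.1 and 9.11 end OS follow-up at patient withdrawal, so the study-level reading loses OS data without contradicting those sections.

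**3. How often the row could apply**

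The documents give no rate for this class of event. The rates *p* below are assumptions, before the clinical-benefit exception. For *n* patients, the expected number is *np* and the chance of at least one is 1 − (1 − *p*)^*n*.

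Phase 2a, *n* = 20 per arm (Protocol 13.2):

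- *p* = 2%: 20 × 0.02 = 0.4 expected; 1 − 0.98^20 = 0.332
- *p* = 5%: 20 × 0.05 = 1 expected; 1 − 0.95^20 = 0.642
- *p* = 10%: 20 × 0.10 = 2 expected; 1 − 0.90^20 = 0.878

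The last two equal the 64% and 88% in the table in 13.2 because the formula is the same. That confirms the arithmetic and says nothing about the true rate.

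Table 8.b is not limited to phase 2a. For phase 1, with about 18 patients over all dose levels:

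- *p* = 2%: 18 × 0.02 = 0.36 expected; 1 − 0.98^18 = 0.305
- *p* = 5%: 18 × 0.05 = 0.9 expected; 1 − 0.95^18 = 0.603
- *p* = 10%: 18 × 0.10 = 1.8 expected; 1 − 0.90^18 = 0.850

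**The case against.** The strongest reply is that context already settles the meaning. Table 8.b sits under dose modification, is headed as recommendations for modakafusp alfa, and has an exception for clinical benefit that makes sense only as a reason to keep dosing. Table 8.c and 8.6.1.5 use *study* just as loosely when they mean treatment. Section 9.8 names an AE as a reason to stop drug and 9.9 does not name one as a reason to leave. To lose data, a site must read a dose table against several explicit follow-up instructions.

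This shows what was probably intended. It does not remove the conflict, because the table still instructs sites in words that the protocol defines elsewhere.

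Other points stand as limits:

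- SAE follow-up is required separately.
- The daratumumab SC option is discretionary and covers only events related to modakafusp alfa alone, so a stricter Grade 4 rule could be read as narrowing it.
- Treated patients are not replaced, and those with only missing or non-evaluable responses stay in the ORR denominator as non-responders.
- No dose comparison is tested.
- The rates in the calculation are assumed.
- The protocol history records a sponsor decision not to proceed to phase 2a. The current text retains phase 2a, and the row applies to phase 1 in any case.

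**Conclusion.** The concern holds. Table 8.b and the text of 8.6.1.3 remove patients from the study for toxicity; 9.9 makes that the end of data collection; and 6.3.1, 9.8 and 9.11 require PFS follow-up to continue. The conflict is clearest for PFS visits and for the 9.8 rule. For OS the problem is possible loss of data.

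The loss is possible rather than certain. It depends on sites taking the table literally and on the clinical-benefit exception not being used. The number of patients is likely to be small: 0.4 to 2 per phase 2a arm at assumed rates of 2% to 10%. In an arm of 20, each patient is 5 percentage points of ORR (1/20). The size and direction of any bias, and any difference between doses, cannot be derived from the documents. Follow-up that is never recorded may not be recoverable later, so the wording should be corrected.

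**What to change.** - **Table 8.b, Grade 4 row:** replace withdrawal from the study with permanent discontinuation of study treatment, keep the clinical-benefit exception, and make it subject to the daratumumab SC option in 8.6.1.5.
- **Section 8.6.1.3:** change the last option to permanent discontinuation of study treatment, subject to the same option.
- **Both places:** state that the end-of-treatment visit and post-treatment follow-up proceed under 9.8 and 9.11.

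*Study treatment* is the safer term, provided the 8.6.1.5 option is named. Writing *modakafusp alfa* alone would leave it unclear whether daratumumab SC stops as well.

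The cost is two phrases and a cross-reference at the next amendment. No stopping threshold changes and no visit is added, since the follow-up is already in the Schedules of Events. The protocol history shows that similar wording on Grade 4 life-threatening events was once added to 8.6.1.5 at a health authority's request and later removed. It does not show where the Table 8.b row came from, so the sponsor should check that before rewording.
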